9.7.2 Main analysis

Analyses will be conducted in line with good statistical practices. Models will use confounding factors to adjust for group differences. However, unmeasured confounding and resulting confounding bias affecting point estimates, confidence intervals and any p-values in the treatment group comparisons may remain.

In a first step, Cox proportional hazards regression models will be applied in in each treatment group compared to phenprocoumon (reference) to estimate crude and confounder adjusted hazard ratios (HRs) of the above mentioned outcomes as well as treatment discontinuation (persistence) with accompanying 95% confidence intervals and *p*-values. Persistence (risk of non-persistence) will also be calculated separately for specific time points of interest (months 3, 6, 9, 12, 18 and 24). In the analysis of reduced vs. standard dose of NOACs, the standard dose will be used as reference. Kaplan-Meier cumulative incidence plots will be generated to characterize risk of outcome events of interest over time.

Information on confounding factors which are planned to be included in the models as well as in the estimation of the propensity score can be found in section 9.3.3.

In a second step, we will use the stabilized inverse probability of treatment weighting (IPTW) approach based on the propensity score to adjust for potential confounding resulting from imbalances in the baseline characteristics of different treatment groups. The objective of IPTW

based analysis is to create a weighted sample, for which the distribution of possible confounding variables is approximately the same between comparison groups (12,13). The propensity score is defined as the patient's probability to receive a treatment under investigation (i.e. phenprocoumon for main analyses and standard dose for the analyses of reduced vs. standard dose of NOACs) given a set of known patient's baseline characteristics. Propensity scores will be calculated using multiple logistic regression on a relevant set of patient characteristics listed in section 9.3.1 for each 1:1 comparison separately, e.g. rivaroxaban vs. phenprocoumon, rivaroxaban 15 mg vs. rivaroxaban 20 mg etc.

Let Z be an indicator variable relating to the treatment received by a patient, Z = 1 for an active treatment (e.g. rivaroxaban), Z = 0 for a control treatment (warfarin), and let X denote a vector of observed patient baseline characteristics. Then the propensity score is e = P(Z = 1|X). The inverse

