probability of treatment weight is defined as $w = \frac{Z}{e} + \frac{1-Z}{1-e}$, i.e.

$$w = \frac{1}{e}$$
 for patients receiving the active treatment, and $w = \frac{1}{1-e}$ for patients receiving the control treatment.

Weighting by the inverse probability of treatment results in an artificial population or synthetic sample, in which treatment assignment is independent of measured baseline characteristics. Of note, a very low propensity score of subjects receiving an active treatment, or a propensity score close to 1 of subjects receiving a control treatment result in large weights. Such weights increase the variability of the estimated treatment effect (12). Moreover, it is known that the sample size of the synthetic sample is always greater that the sample size of the original data. Consequently, regression estimates with IPTW tend to have smaller confidence intervals because of the inflated sample sizes. In our analysis we will use IPTW with stabilized weights (12,13) which ensure more robust effect estimates. The stabilized weight is defined as $sw = \frac{P(Z=1)*Z}{e} + \frac{(1-P(Z=1))*(1-Z)}{1-e}$. The use of stabilized weights in the synthetic data preserves the sample size of the original data set (12). The application of propensity score methods via stabilized weights requires overlap of the propensity score distribution in the active and control treatment group. Therefore distributions of propensity scores will be inspected for original data and the synthetic sample. Furthermore, the distribution of stabilized weights in the original data will be examined to determine, if large weights remain after stabilization of weights. By applying IPTW method using the propensity score assessment needs to be done, whether weighting procedure succeeded to balance patient characteristics between treatment groups. The distributions of propensity scores and stabilized weights will be inspected for original data and the synthetic sample. The balance of patient characteristics between treatment groups will be checked by using standardized mean differences (SMD). An absolute SMD of 0.1 or less will be considered as a negligible difference between groups. For continuous variables, the SMD is calculated via

$$SMD_{cont} = \frac{\overline{X_T} - \overline{X_C}}{\sqrt{\frac{S_T^2 + S_C^2}{2}}},$$

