Where $\overline{X_T}$, S_T^2 and $\overline{X_C}$, S_C^2 denote the weighted sample mean and weighted sample variance of the variable in the treated and control patients, respectively. For binary variables, the SMD is calculated by

$$SMD_{cat} = \frac{100(P_T - P_C)}{\sqrt{(P_T(1 - P_T) + P_C(1 - P_C))/2}},$$

Where P_T and P_C denote the weighted sample prevalence of the variable in the treated and control patients, respectively.

In a third step, we will additionally conduct a propensity score matched analyses for each comparison. A 1:1 matching will be performed using the nearest-neighbor approach with a caliper of 0.2 without replacement. Again, the balance of patient characteristics between treatment groups will be checked in analogy to the description above.

For the analysis of IS /SE as combined endpoint and ICH (primary objectives) as well as for the comparison of reduced vs. standard dose of NOACs (other objectives) all three approaches will be used, i.e. Cox proportional hazards regression models, IPTW and propensity-score matching. For all other analyses (secondary objectives) only Cox proportional hazards regression models and IPTW will be applied.

To describe the risk of recurrent hospitalizations and IS/ SE, the following analyses will be conducted. Analyses of recurrent events will be conducted for the unadjusted, matched as well as IPTW populations:

1) Mean cumulative function (MCF)

An important quantity is the mean number of recurrent events per subject by a certain time, i.e. the mean cumulative function (MCF) which is defined as

$$\mu(t) = E(N(t)).$$

The MCF is a marginal quantity, i.e. independent of the history of the event process. The common Nelson-Aalen estimator for survival analysis can be used as a non-parametric estimator for the MCF under the assumption of independent censoring, i.e. patients remaining are representative of the population.

Let $Y_i(t)$ indicate whether patient i = 1, ..., m is "at risk" for an event at time t and $Y_{\Sigma}(t) = \sum_{i=1}^{m} Y_i(t)$ the total number of patients at risk at time t. With $dN_{\Sigma}(t) = \sum_{i=1}^{m} Y_i(t)dN_i(t)$ being the total number of events at time t and H distinct event times across all m patients denoted as $t_1 \leq \cdots \leq t_H$ the Nelson-Aalen estimator is given as

 $\hat{\mu}(t) = \sum_{h:t_h \le t} \frac{dN_{\Sigma}(t_h)}{Y_{\Sigma}(t_h)}.$

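### The binary SMD carries a factor of 100 against one balance limit of 0.1, so the check on binary covariates is 100 times too strict; separately, prose and formula disagree on which treatment the propensity score predicts.

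*Protocol*

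**What the plan says.** All of this stands in Protocol section 9.7.2.

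- **Balance rule.** "An absolute SMD of 0.1 or less will be considered as a negligible difference between groups". This is the only limit given, and it is not split by type of variable.
- **SMD formulas.** The continuous SMD is the difference in weighted means over the pooled standard deviation, with no multiplier. The binary SMD begins "SMD_{cat} = \frac{100(P_T - P_C"; P_T and P_C are defined as weighted prevalences. The same check is to be repeated after matching.
- **Score, in prose.** The propensity score is the "probability to receive a treatment under investigation (i.e. phenprocoumon for main analyses and standard dose" for the dose comparison.
- **Score, in the formula block.** "Z = 1 for an active treatment (e.g. rivaroxaban), Z = 0 for a control treatment (warfarin", followed by "Then the propensity score is e = P(Z = 1|X". Active patients are weighted by 1/e and controls by 1/(1−e), then: "In our analysis we will use IPTW with stabilized weights".
- **Reference group.** The Cox models are fitted "in each treatment group compared to phenprocoumon (reference" group, and standard dose is the reference for the dose comparison. Warfarin is not a comparator; its use is an exclusion criterion (section 9.2.3).
- **Score covariates.** One paragraph points to section 9.3.3 (covariates), a later one to section 9.3.1 (exposure definition).

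**The concern.** The balance check is how the study would show that weighting and matching removed the measured differences between groups. Most of the comorbidities and comedications in section 9.3.3 are binary. If the limit for them is 100 times too strict, a failure no longer separates poor balance from good balance. IPTW is planned for every objective, and matching for the primary objectives and the dose comparison, so the faulty rule applies throughout.

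The conflict over direction matters because the prose says which probability to model and the next paragraphs say how to turn it into a weight. A programmer who takes the score from one and the formula from the other gets weights that add confounding. The printed binary check would not help to catch this, since it can fail under correct weights too.

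**Working it through.** **1. The binary SMD against the 0.1 limit**

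Inputs: the section 9.7.2 formula and limit; group sizes of 30,200 rivaroxaban and 35,400 phenprocoumon (section 9.5).

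*Example, 21% versus 20%.* Denominator: √[(0.21×0.79 + 0.20×0.80)/2] = √0.16295 = 0.4037. Without the factor: 0.01/0.4037 = 0.025. With it: 2.48.

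*Difference that just meets 0.1*, solving the formula for P_T − P_C:

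| Prevalence | Without factor 100 | As printed |
|---|---|---|
| 5% | 2.4 points | 0.02 points |
| 20% | 4.1 points | 0.04 points |
| 50% | 5.0 points | 0.05 points |

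*Chance benchmark.* Under random allocation the unscaled SMD has a standard error of about √(1/30,200 + 1/35,400) = 0.0078, or 0.78 as printed. The chance of falling within ±0.1 is P(|N(0,1)| < 0.1/0.78) ≈ 0.10. The primary population has renal impairment and is smaller. With the sizes of the earlier renal-impairment subgroup shown in section 7 (2,786 versus 9,871), the standard error is √(1/2,786 + 1/9,871) = 0.0215 and the pass rate about 4%.

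*Simulation.* One confounder, an assumed log-odds slope on treatment of 0.25, 0.5 or 1.0 per SD, 65,600 patients, and weights from the true score. A related binary covariate, correctly weighted, scored 0.75, 0.24 and 0.26 on the printed scale. All three exceed 0.1, although the unscaled values are below 0.01.

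**2. The direction of the score**

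Take a covariate pattern with P(rivaroxaban | X) = 0.1. The overall share on rivaroxaban is 30,200/65,600 = 0.460.

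| Coding | Rivaroxaban patient | Phenprocoumon patient |
|---|---|---|
| Formula block as printed, e = 0.1 | 0.460/0.1 = 4.60 | 0.540/0.9 = 0.60 |
| Prose score put into that formula, e = 0.9 | 0.460/0.9 = 0.51 | 0.540/0.1 = 5.40 |

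The second row keeps the printed numerators and changes only e. Each arm then receives the other arm's score-based factor.

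In the same simulation the confounder's SMD was:

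| Slope | Crude | Formula block | Prose score in formula | Sum of weights / n (prose score) |
|---|---|---|---|---|
| 0.25 | 0.24 | about 0 | 0.49 | 1.06 |
| 0.5 | 0.48 | about 0 | 0.99 | 1.16 |
| 1.0 | 0.91 | about 0 | 2.00 | 1.71 |

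Relabelling both Z and e to phenprocoumon gave weights identical to the formula block. The fault therefore lies only in mixing the two definitions.

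**The case against.** **The factor 100 is a diagnostic slip.** It enters no weight, match or hazard ratio. It raises false alarms and cannot pass a real imbalance. Continuous covariates are unaffected, no action is tied to a failed check, and values 100 times too large would probably be noticed. All of this stands, and it limits the harm to a check that does not work as printed. The 10% and 4% pass rates are also a chance benchmark: a well-fitted score that contains the covariate can balance it more tightly than chance after weighting, so more covariates could then pass. The mismatch of scale remains.

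**A reader might infer that the planned weights are inverted.** The document does not support that. Z, e, the weights and the accompanying explanation of when weights become large all agree, and coded on their own they are right. Only the parenthesis in the prose is out of line. A mix-up would also leave traces in the continuous SMDs, in the weight distributions that the section says will be inspected, and in a sum of weights above n.

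**A reader might infer that the matches are wrong**, because the plan gives a "nearest-neighbor approach with a caliper of 0.2 without replacement" and no scale. That does not follow either. Only the raw-probability reading left a residual SMD above 0.1 in the simulation (0.04, 0.18 and 0.18 for the three slopes). The raw logit left at most 0.017, and 0.2 SD of the logit at most 0.009. The scale is a detail that the SAP can supply.

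**The SAP is still to come.** Section 9.7.3 says it will supplement this concept. That excuses omissions, but not a printed formula that disagrees with its own limit or two opposite definitions of one quantity.

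**Conclusion.** The point holds in two parts.

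First, the balance rule for binary covariates is wrong as written. Its scale is off by 100, and this follows from the printed text without any assumption. The resulting pass rates (about 10% at 30,200 versus 35,400; about 4% at the earlier subgroup's sizes) assume balance no better than random allocation. The rule spoils the evidence that adjustment worked, but not the hazard ratios themselves. The adjusted Cox models of the first step use no propensity score.

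Second, the prose and the formula block contradict each other on the direction of the score, and the control is misnamed. Weights go wrong only if the two are combined; the sizes shown for that case rest on assumed confounder strengths. The double reference for the score covariates is a minor slip in the same section. The caliper is not part of the finding.

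**What to change.** - Delete the factor 100 from the binary SMD and keep the limit of 0.1. Alternatively, report both SMDs in percent with a limit of 10.
- Define the score once: e = P(NOAC | X) for comparisons with phenprocoumon and e = P(reduced dose | X) for the dose comparison. Set Z = 1 for that group and Z = 0 for phenprocoumon or standard dose, and remove warfarin from the definition.
- Change the covariate reference from 9.3.1 to 9.3.3 and limit it to baseline items. Section 9.3.3 also lists duration of follow-up and type of cohort exit, which are known only after the index date.
- Optional: state the caliper scale here or in the SAP.

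The cost is a few edits to wording and one formula. Sample size, data and the choice of analyses do not change.

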One treatment effect estimate, which can be seen as an 'average effect' will be obtained. This average effect, however, is difficult to interpret, as for example the effect on the second event already includes the effect on the first event. Averaging the WLW treatment effects for first and second event would thus seem to double-count the effect on the first event.

Therefore, it is generally more advisable to obtain event-specific estimates by means of specifying interactions in the PROC PHREG call routine, i.e. treatment by event number. The following code gives an example of this for k = 3.

```
PROC PHREG DATA=<dataset> COVSANDWICH(AGGREGATE);
MODEL totstop*event(0) = treat1 treat2 treat3;
treat1 = treat*(num=1);
treat2 = treat*(num=2);
treat3 = treat*(num=3);
STRATA num;
ID pid;
RUN;
```

The event-specific estimate for the first event then coincides with the estimate of the Cox proportional hazards model for time-to-first event.

The distinctive feature of the WLW model is that each individual's time at risk for each event is considered to study entry, so that study entry is 'preserved' for all event-specific analyses.

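### Stabilised weights remove the sample-size inflation but do not correct the variance, so the IPTW Cox intervals can still be too narrow unless a robust variance is stated

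*Protocol*

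**What the plan says.** Section 9.7.2 of the protocol reports hazard ratios "with accompanying 95% confidence intervals and *p*-values". For the IS/SE and ICH outcomes of the primary objectives "all three approaches will be used, i.e. Cox proportional hazards regression models, IPTW and propensity-score matching"; the secondary objectives use only Cox regression and IPTW.

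The same section names a problem with plain inverse-probability weights: "regression estimates with IPTW tend to have smaller confidence intervals because of the inflated sample sizes". The next sentence gives the response: "In our analysis we will use IPTW with stabilized weights (12,13) which ensure more robust effect estimates". The property then claimed for them is that "The use of stabilized weights in the synthetic data preserves the sample size of the original data set". The section also notes that large weights raise the variability of the effect estimate. It plans that "the distribution of stabilized weights in the original data will be examined to determine, if large weights remain after stabilization of weights", but attaches no consequence for the variance.

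No variance estimator is named for the weighted Cox models. Robust standard errors appear only under the recurrent-event model, in its title and in its sample code ("PROC PHREG DATA=<dataset> COVSANDWICH(AGGREGATE"). Section 9.7.3 says a more detailed SAP will supplement this concept.

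**The concern.** Read in order, the paragraph tells the analyst that over-narrow IPTW intervals come from an inflated sample, and that stabilised weights restore the sample size. The natural inference is that interval width is then settled. It is not. Two separate things make a model-based variance wrong in a weighted Cox model: the total weight exceeds N, and the weights differ between patients. Stabilisation deals only with the first.

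The objection is therefore to reasoning that is on the page, not to silence. Section 9.7.2 does fix the variance for the recurrent-event model, and for the weighted Cox models it gives a rationale suggesting that nothing more is needed. If that premise carries into the programming, reported 95% intervals for IS/SE and ICH could cover less often than stated, most where treated and control patients overlap least.

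**Working it through.** **Inputs from the protocol.** Earlier renal-impairment subgroup (section 7, table above Figure 1): 2,786 rivaroxaban 15 mg and 9,871 phenprocoumon, so N = 12,657 and p = 2,786/12,657 = 0.220; phenprocoumon rates 3.39 (IS) and 0.99 (ICH) per 100 person-years. Average follow-up one year (section 9.5). I use these sizes as a stand-in, because section 9.5 sizes only the overall population.

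**The plan's own figures.** Table 3 is users × rate × 1 year: phenprocoumon 35,400 × 0.007 = 247.8 and × 0.025 = 885.0; apixaban 16,800 × 0.004 = 67.2 and × 0.027 = 453.6; rivaroxaban 30,200 × 0.005 = 151.0 and × 0.022 = 664.4; edoxaban 1,600 × 0.004 = 6.4 and × 0.022 = 35.2. All eight counts reproduce, and the limits agree within one event. There is no figure on IPTW variance to reproduce.

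**Step 1: what stabilisation does.** With e the propensity score:
- Plain weights: E[Z/e + (1−Z)/(1−e)] = 1 + 1 = 2, so they sum to about 2N.
- Stabilised weights: the expectation is p + (1−p) = 1, so they sum to about N.

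The simulation gave 2.00 and 1.00. The sentence in 9.7.2 about preserving the sample size is correct.

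**Step 2: what it leaves.** For a rare event and a true HR of 1, the variance contributed by one arm is about Σw²/(Σw)² over that arm's patients with events. The model-based formula uses 1/Σw. The two agree only if Σw² = Σw.

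Take a standard normal confounder score x, log-odds of active treatment a + g·x, log-hazard b·x, and a chosen so that the mean propensity is p. With r = model-based SE / true SE,

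r² = {1/[p(1−p)]} / {2 + 2·exp(g²/2)·cosh(a + g·b)}, where 1/[p(1−p)] = 5.83.

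For g = 1.0, b = 0: a = −1.509; the denominator is 2 + 2 × 1.649 × 2.372 = 9.82; r = √(5.83/9.82) = 0.77. Coverage is then about 2Φ(1.96 × 0.77) − 1 = 86.9%. For the other rows a = −1.290, −1.360 and −1.755.

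**Step 3: simulation.** IS rate, HR 1, logistic propensity score estimated on 5 normal covariates, stabilised weights, 1,000 replicates per scenario (Monte Carlo SE near 95% is √(0.95 × 0.05/1000) = 0.7 points). The values of g and b are assumptions; the protocol gives none. Effective sample size (ESS) is (Σw)²/Σw². Cells list b = 0, 0.5, 1.0.

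| Imbalance (g) | ESS/N | r, formula | r, simulated | Coverage %, model-based | Coverage %, sandwich |
|---|---|---|---|---|---|
| Weak (0.3) | 0.98 | 0.98, 1.02, 1.06 | 0.98, 0.99, 1.06 | 95.1, 95.0, 95.9 | 95.6, 94.3, 94.2 |
| Moderate (0.6) | 0.93 | 0.91, 1.00, 1.07 | 0.87, 0.96, 1.03 | 91.0, 93.5, 94.9 | 93.3, 93.7, 94.0 |
| Strong (1.0) | 0.81 | 0.77, 0.90, 1.01 | 0.77, 0.91, 1.00 | 86.8, 92.3, 94.3 | 94.0, 95.4, 94.9 |
| Very strong (1.5) | 0.56 | 0.54, 0.71, 0.84 | 0.60, 0.71, 0.83 | 76.5, 84.6, 89.8 | 94.0, 94.2, 95.6 |

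The effective sample size falls to 0.56 N while the weights still sum to N. With plain weights, model-based coverage in the same scenarios was 49% to 79%, so stabilisation helps but does not finish the job. The relief from prognostic covariates (larger b) arises because g and b have the same sign here. As a is negative, opposite signs would raise the cosh term and lower r.

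**Step 4: other settings, model-based with stabilised weights.**
- Renal ICH (600 replicates, g 0.3 to 1.0, b = 0.5): r 0.89 to 1.00, coverage 92.2% to 94.8%.
- Overall rivaroxaban IS/SE, 30,200 versus 35,400 (200 replicates, so noisier): r 0.79 to 1.03, coverage 86.0% to 95.5%.
- Small treated share, as for edoxaban, in a separate simulation with 800 replicates and weight CV 0.33 and 0.68: model-based coverage 89% and 79%; sandwich 93% and 91%.

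**The case against.** **The protocol never says a model-based variance will be used.** This is the strongest objection and it stands. A reader might infer that the IPTW intervals will be too narrow; the document does not support that. Sections 9.7.2 and 9.7.3 leave the estimator open, and the SAP may specify a sandwich or bootstrap variance.

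**The direction is not fixed.** This also stands. Under weak imbalance, or up to strong imbalance with strongly prognostic covariates, model-based intervals in these runs were about right or slightly wide (r up to 1.06).

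**Nothing in 9.7.2 is false as written.** Largely true. A reader might take the section to assert that stabilisation resolves the interval problem, but no sentence says so, and the claim about sample size is correct. The section also concedes that large weights may remain. What does not fall away is that an over-narrow interval is raised as a problem and met only with a device that cures half of it.

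**Robust errors are partly present.** The recurrent-event analyses also run in the IPTW population, and the first-event estimate is said to match the time-to-first-event Cox model. If run with weights, that code would give a robust SE for first IS/SE. It does not reach ICH, and the sample code has no weight statement.

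**Stakes are limited.** IPTW is one of three approaches for the primary outcomes, and the abstract declares p-values and intervals non-confirmatory. That lowers the consequence; it does not make a mislabelled 95% interval acceptable.

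A reader might extend the point to the 1:1 matched analysis. The protocol makes no claim about variance there, so that is ordinary SAP detail and not part of this point.

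**Conclusion.** The point holds as a conditional one. Section 9.7.2 offers stabilised weights as the only response to over-narrow IPTW intervals, and they remove only the sample-size inflation. With a model-based variance and no further correction, the nominal 95% intervals can be too narrow when the weights vary. At the earlier study's renal group sizes, coverage was 76.5% to 94.9% across moderate to very strong imbalance and 95.0% to 95.9% under weak imbalance; the sandwich variance gave 93.3% to 95.6% in all 12 scenarios.

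These figures rest on a true HR of 1, one year of follow-up, normal covariates and assumed strengths of confounding. The protocol gives no propensity-score overlap or weight distribution, so the real size cannot be derived from it. The document shows a misleading rationale; it does not show that the final intervals will under-cover.

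**What to change.** In section 9.7.2, after the description of stabilised weights, state that stabilisation removes only the sample-size inflation. Add that all IPTW-weighted Cox models use a robust (sandwich) variance, or a bootstrap that re-estimates the propensity score in each resample. If the SAP already specifies this, align 9.7.2 with it.

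The cost is a sentence or two and, for the sandwich, a software option that the protocol's own recurrent-event code already uses; a bootstrap costs computing time. Some intervals will become slightly wider. With few treated patients, as for edoxaban, the sandwich may still under-cover a little (93% and 91% in the small-share runs), so the bootstrap is worth considering there.

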9.2.3 Exclusion criteria

Patients meeting any of the following exclusion criteria (see Annex 3: Additional information) will be excluded from the analysis:

• A verified ambulatory or primary/ secondary hospital discharge diagnosis of valvular atrial fibrillation in the baseline period;

- A verified ambulatory or primary/ secondary hospital discharge diagnosis indicating pregnancy in the baseline period;
- A verified ambulatory or primary/ secondary hospital discharge diagnosis of a transient cause of atrial fibrillation in the baseline period;
- A verified ambulatory or primary/ secondary hospital discharge diagnosis of venous thromboembolism (VTE) in the previous or same quarter of the index date;
- A claim for hip or knee replacement surgery in the 60 days prior to or on the index date;
- A prescription of heparin or fondaparinux in the 60 days prior to or on the index date;
- A prescription of more than one oral anticoagulant (rivaroxaban, apixaban, edoxaban or phenprocoumon) on the index date;
- A prescription of warfarin or dabigatran in the baseline period or on the index date;
- A verified ambulatory or primary/ secondary hospital discharge diagnosis of end-stage kidney disease or a claim for dialysis in the baseline period;
- Patients receiving an initial dose of rivaroxaban 10 mg/ 2.5 mg or edoxaban 15 mg (these dosages are not indicated for the treatment of NVAF).
- A prescription of contraindicated drug for apixaban or rivaroxaban due to drug interactions (i.e. azole antifungals and HIV protease inhibitors) in the 60 days before or on the index date.

For the main analysis, patients will be followed from the index date until the first diagnosis of the respective outcome event, discontinuation of the index drug, death, end of continuous insurance in the SHI or the end of the study period (31 December 2017), whichever comes first. Patients will be censored in all analyses if they switch to phenprocoumon or another NOAC (including dabigatran), receive a prescription of heparin/ fondaparinux, warfarin, rivaroxaban 10 mg/ 2.5 mg, edoxaban 15mg or a contraindicated drug as defined above. For specific analyses, the end of follow-up may differ as described in 9.3.1.

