In SAS the Nelson-Aalen estimator for the MCF can be calculated by means of the PHREG procedure. The following code plots the estimated MCFs of several treatment groups in one graph:

```
PROC PHREG DATA=dataset PLOTS(OVERLAY=ROW)=MCF;
MODEL (TStart,TStop) * Status(0)= ;
* start/stop time of inter-event times and censoring
identifier;
STRATA trt; * treatment group identifier;
RUN;
```

2) Andersen-Gill Model (AG) with robust standard errors (Wei Lin Weissfeld Model)

The Wei Lin Weissfeld (WLW) model models the total time from randomization to 1^{st} , 2^{nd} , 3^{rd} , ..., k-th event. Before applying the WLW model one has to pre-specify the maximum number of events k one wants to analyze. Therefore, one has to arrange the data in the right structure (a semi-restricted risk set) and also make sure to create 'dummy' events for patients with fewer than the maximal number of events k.

Semi-restricted risk sets

Semi-restricted risk sets have event-specific baseline hazards but allow subjects who have less than (k-1) events to be at risk for the *k*-th event through the creation of 'dummy' risk intervals. Thus a subject who has had none or one event can be considered at risk of a fourth event. However, a semi-restricted risk set does not allow information from the *k*-th event risk interval to contribute to the risk set for an earlier event. This risk set only applies to the total time and counting process formulation with event-specific baseline hazards.

[figure not shown]

Figure 2 Hypothetical example with total time risk intervals

ID	time	num	event	total		total cp	
				start	stop	start	stop
Α	2	1	1	0	2	0	2
Α	5	2	1	0	5	2	5
A	13	3	0	0	13	5	13
в	7	1	1	0	7	0	7
в	11	2	1	0	11	7	11
в	17	3	1	0	17	11	17
С	14	1	0	0	14	0	14
С	14	2	0	0	14	0	14
С	14	3	0	0	14	0	14

Figure 3 Semi-restricted risk sets in dataset representation

For example, in total time subject B is included with the second event time and subject C is included with a 'dummy' risk interval in the risk set for the second event of subject A (Figure 1). In the example above the maximum number of events per patient is three (for subject B). Accordingly, two dummy risk intervals need to be included for subject C for 'dummy' event number two and three. This results in a dataset as displayed in Figure 2.

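### The recurrent-event section names one model and specifies another, its follow-up rule conflicts with counting later events, and its absolute-risk curves make no allowance for death

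*Protocol*

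**What the plan says.** Recurrent hospitalization and recurrent IS/SE are secondary objectives (Protocol section 8.2). Section 9.3.2 defines when a further hospitalization counts as a recurrence. Section 9.7.2 plans two analyses.

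- **MCF.** The target is the mean number of events per subject by time t. Nelson-Aalen is named as "non-parametric estimator for the MCF under the assumption of independent censoring, i.e. patients remaining are representative of the population".
- **Regression model.** The title is "Andersen-Gill Model (AG) with robust standard errors (Wei Lin Weissfeld Model". The text then describes time from study entry to each successive event: "Semi-restricted risk sets have event-specific baseline hazards but allow subjects who have less than (k-1) events to be at risk for the" k-th event. It adds dummy intervals and gives code with "MODEL totstop*event(0) = treat1 treat2 treat3", stratified by event number. It says one average effect will be obtained, warns that averaging would count the first event twice, and calls event-specific estimates more advisable.

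For outcome events in general, section 9.7.2 says "Kaplan-Meier cumulative incidence plots will be generated to characterize risk of outcome events of interest over time".

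The follow-up rule stands at the end of section 9.2.3. In the main analysis patients are followed "until the first diagnosis of the respective outcome event, discontinuation of the index drug, death", end of insurance or end of study. It adds: "For specific analyses, the end of follow-up may differ as described in 9.3.1".

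**The concern.** There are three faults of unequal strength.

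1. **Model.** Andersen-Gill (AG) uses counting-process intervals, one baseline hazard and one common rate ratio. WLW uses total time, a separate baseline for each event number and dummy intervals, and yields a hazard ratio for each event. An analyst who follows the title and one who follows the code will report different quantities.
2. **Follow-up.** The recurrent analyses stand under the heading Main analysis, and the main-analysis rule stops at the first outcome event. Taken literally, that rule conflicts with sections 9.3.2 and 9.7.2, which need later events.
3. **Death.** A patient who has died can have no further stroke or admission. If death is handled like any other end of follow-up, the curves describe a population in which nobody dies. They then exceed the share of patients who actually have the event and the mean number of events they have. If mortality differed between drugs, the excess would differ too.

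The first two faults touch secondary outcomes. The third also reaches the Kaplan-Meier plots of the primary outcomes.

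**Working it through.** **Model.** The data example in section 9.7.2 (Figure 3) has three subjects: A with events at 2 and 5, end 13; B with events at 7, 11 and 17; C with no event, end 14.

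- AG needs A 3 + B 3 + C 1 = 7 rows. The printed table has 9, because C's interval 0 to 14 appears three times. That is the WLW layout; an unstratified AG fit to it would count C three times.
- The gap shows in results. In a simulation (true rate ratio 0.80, 1 event per person-year, no frailty, 5 runs of 4,000 subjects), AG gave 0.82, and WLW gave 0.82, 0.74 and 0.62 for events 1, 2 and 3. Both are correct for their own target.

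**Follow-up.** Section 9.3.1, where the exception points, contains the exposure, discontinuation and switching rules. Its only analysis-specific rule is censoring at a change between reduced and standard dose. Putting the same example through the protocol's own MCF formula (events divided by number at risk, summed):

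- Full follow-up: 1/3 + 1/3 + 1/3 + 1/3 + 1/1 = 2.333 at time 17, from 5 events.
- Stopped at first event: 1/3 + 1/2 = 0.833, from 2 events.

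**Death.** The protocol gives no figure to reproduce here. Inputs:

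- event rate λ = 0.034 per person-year (ischaemic stroke, rivaroxaban 15 mg, renal impairment, Figure 1 in section 7);
- death rate μ = 0.05, 0.10 or 0.20 per person-year. This is an assumption, as the protocol states no mortality;
- rates constant and independent.

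Formulas:

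- Kaplan-Meier: 1 − exp(−λt). Cumulative incidence with death as competing event: λ/(λ+μ) × (1 − exp(−(λ+μ)t)).
- MCF with death as censoring: λt. With death as terminal event: λ(1 − exp(−μt))/μ. The ratio is μt/(1 − exp(−μt)), whatever λ is.

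| t | μ | Kaplan-Meier | with death | ratio | MCF ratio |
|---|---|---|---|---|---|
| 1 y | 0.05 | 3.34% | 3.26% | 1.03 | 1.03 |
| 1 y | 0.10 | 3.34% | 3.18% | 1.05 | 1.05 |
| 1 y | 0.20 | 3.34% | 3.03% | 1.10 | 1.10 |
| 4 y | 0.05 | 12.7% | 11.6% | 1.10 | 1.10 |
| 4 y | 0.10 | 12.7% | 10.5% | 1.21 | 1.21 |
| 4 y | 0.20 | 12.7% | 8.8% | 1.44 | 1.45 |

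Example: at 4 years and μ = 0.10, 0.034/0.134 × (1 − exp(−0.536)) = 0.105, against 1 − exp(−0.136) = 0.127.

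**The case against.** The defence has real force on several points.

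- **A reader might infer that the recurrent objectives have no defined estimate.** That goes too far. The MCF has a target, a formula and code, and the event-specific WLW estimates have code with clustered variance. What is open is which effect is reported and under which name.
- **A reader might infer that no second event would ever be observed.** The text does not bear that out. Section 9.3.2 defines recurrences, the MCF code uses start and stop times, and the worked example follows A and B past their first events. The intent is plain; the rule and its cross-reference fail to express it.
- **A reader might fault the missing k**, since "Before applying the WLW model one has to pre-specify the maximum number of events k one wants to analyze". The value 3 appears only in a code example. Section 9.7.3 defers detail to the SAP, and k can properly be fixed there.
- **A reader might conclude that AG should replace WLW.** Nothing in the protocol requires it. AG would censor at death as well.
- **On death,** no sentence says outright that it is independent censoring; this follows from reading sections 9.2.3 and 9.7.2 together. Section 9.9 mentions death before hospitalization as a limitation and says the objectives concern relative risks. The 4-year figure lies far beyond the 1-year average follow-up assumed in section 9.5, and mean follow-up in Figure 1 is about 219 to 421 days.

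These points limit the size and reach of the concern. They do not remove the wrong model title, the conflicting follow-up rule or the upward bias of the curves.

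**Conclusion.** The point holds in three limited parts. The model title is wrong on its face, and the reported effect is left between an average and event-specific estimates. The follow-up rule contradicts the recurrent-event definitions and needs reconciling, though this is not evidence that recurrences would be dropped. The curves overstate absolute risk and mean event count by about 5% at 1 year (2.5 to 10%) and about 21% at 4 years (10 to 45%), for an assumed death rate of 10 per 100 person-years (5 to 20). In absolute terms the stroke curve is too high by about 0.16 percentage points at 1 year and 2.2 at 4 years. These sizes rest on the assumed mortality and on constant, independent rates. The Cox hazard ratios are not affected and can be read as cause-specific. The SAP may add detail, but it cannot comply with two conflicting statements, so the protocol text should be corrected.

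**What to change.** 1. Make the title in section 9.7.2 match the model fitted, and state which estimate is reported. Either keep event-specific WLW estimates as coded, or use an AG rate ratio with counting-process rows, no dummy rows and sandwich variance clustered on patient.
2. State in section 9.2.3, or in section 9.3.1 where the exception points, that for recurrent hospitalization and recurrent IS/SE follow-up continues past the first event until one of the other listed censoring reasons.
3. Replace one minus Kaplan-Meier by the Aalen-Johansen cumulative incidence with death as a competing event. Replace the MCF by the death-adjusted Ghosh-Lin estimator, which weights each Nelson-Aalen increment by the estimated probability of being alive. Table 2 in section 9.4 lists date of death, so no new data are needed.
4. Leave the Cox models as planned and describe their hazard ratios as cause-specific.

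The cost is a few sentences, some extra programming with standard SAS or R procedures, and slightly lower curves.
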